### 1.3 Investigational Device Packaging And Labelling

The Sponsor will be responsible for the packaging of the study products. The study product will be provided free of charge by CairnSurgical, Inc.

The study device is packaged in boxes, and it will be sent to the Investigational sites as follow:

- 1 BOX containing the BCL kit:
  - one (1) sterile BCL model;
  - up to six (6) BARD® GHIATAS® Beaded Breast Localization Wires (patient-specific sizes; sizes are limited to 5 cm, 7 cm, 9 cm, or 14 cm);
  - medical grade permanent marking pen and ruler (Viscot Medical, LLC Sterile Reg/Fine Tip XL Prep Resistant Ink Marker).

Due to the patient specific nature of the device, one additional BCL is provided should it be needed. The BCL model is for single use only. Do not reuse. Do not re-sterilize.

- 1 BOX containing the MRI Accessory Kit with ten (10) pouches, with each pouch containing:
  - one (1) medical grade permanent marking pen and ruler (Viscot Medical, LLC Sterile Reg/Fine Tip XL Prep Resistant Ink Marker)

	Study Title	An Interventional, Post-Market Study to Evaluate the Performance of a Custom-made Medical Device, "Breast Cancer Locator Guidance (BCL)" System, in Breast-conserving Surgery (BCS)		
	Study ID	CS-BCL-EU2021	Sponsor	CairnSurgical Inc.
	Date	25Nov2022	Version	1.0 Substantial Amendment 1_GERMANY

- three (3) 3M™ Tegaderm™ Transparent Dressing
- five (5) Izi Medical Products MRI fiducial markers

The MRI Accessory Kit is used to create the alignment reference points for the subsequent design of the BCL via MRI imaging. The marking pen, fiducial markers, and the Tegaderm™ transparent dressing are intended for single patient use.

Do not re-sterilize.

- 1 BOX containing the MRI Coil Pad with two (2) pouches, with each pouch containing:
  - MRI Coil Pad

The Coil Pad is used during MRI imaging process. Do not re-sterilize any part of the Kit.

The label on the primary and the secondary packaging respectively will contain all necessary information for the traceability of the investigational product, such as:

- patient identifier
- details identifying use, such as anatomical location
- final design iteration or version used to produce the device
- precaution that the patient should be surveyed for potential anatomical changes prior to the procedure
- batch number
- expiry date
- sponsor/manufacturer details
- storage conditions.

The label will also contain the instructions and statement that the IP is intended for clinical research only.

### **Patient-Specific Information Sheet**

Ensure the information on the patient-specific information sheet matches the Subject ID number on the BCL model, and the medical record for the patient undergoing the surgery. The patient-specific information sheet provided with this BCL System consists of the following information:

- Subject ID Number assigned by CairnSurgical. The identical Subject ID Number is printed on the physical BCL model. Ensure that the Subject ID Number on the patient-specific information sheet and BCL match.
- Closest distance from the breast skin to the tumor in millimeters (mm).
- Closest distance from the tumor to the chest wall in mm.
- Patient specific needle length (mm).
- Unique URL address to access and visualize the 3D BCL and anatomical models using CairnSurgical.
- Needle target depth for each port present on BCL.

#### **1.3.1 Product Accountability**

	Study Title	An Interventional, Post-Market Study to Evaluate the Performance of a Custom-made Medical Device, "Breast Cancer Locator Guidance (BCL)" System, in Breast-conserving Surgery (BCS)		
	Study ID	CS-BCL-EU2021	Sponsor	CairnSurgical Inc.
	Date	25Nov2022	Version	1.0 Substantial Amendment 1_GERMANY

Each site will be provided with MD inventory and accountability forms to maintain accurate written documentation of all products transfer processes between the Sponsor, the site, the Investigator, and the patient enrolled. The MD inventory form will be used to document when and how many MDs are delivered to the study site. Site staff has to countersign the form to confirm date of receipt and amount received.

The study product provided for this study will be used only as directed in this study protocol. The Principal Investigator (or delegates) will indicate the date of the surgical procedure and fill the information in the Subject IP Accountability Form for each patient. At the end of the clinical investigation and/or before the expiration date, any partially used/unused component must be returned to Sponsor for destruction. Dispose of used BCL System components in accordance with applicable local, state, and federal laws and regulations.

### 1.3.2 Blinding/Unblinding

Considering the design of the study a blinding/unblinding procedure is not required.

### 1.3.3 Randomization

Considering the design of the study a randomization procedure is not required.

### 1.3.4 Compliance

Considering the design of the study (i.e., the procedure will be performed by the Principal Investigator), a procedure for the evaluation of the compliance is not required.

### 1.3.5 Concomitant Pharmacological Therapies

All concomitant medications should be registered on the appropriate page in the electronic case report form (eCRF) with the dosage and the medication (active substance).

There are no contraindications to the use of any other concomitant medication during the study. Post-operative pain medications will be prescribed as per standard of care.

## 1.4 JUSTIFICATION FOR THE DESIGN OF THE CLINICAL INVESTIGATION

The introduction of national mammographic screening programs has led to an increased number of identified non-palpable breast lesions, and, accordingly, an increased need for preoperative localization of the lesions. The increase reflects detection of small invasive breast cancers (IBCs) and of ductal carcinoma in situ (DCIS), which were rarely detected before the introduction of mammographic screening owing to lack of clinical symptoms. Patients diagnosed with DCIS represent 15% to 20% of cancers detected via mammographic screening, with variations between countries [5]. These patients are often eligible for breast-conserving

*This document is confidential and is to be distributed for review only to investigators, potential investigators, consultants, study staff, and applicable Independent Ethics Committees National Competent Authorities or Institutional Review Boards. The contents of this document shall not be disclosed to others without written authorization from CairnSurgical, Inc.*

	Study Title	An Interventional, Post-Market Study to Evaluate the Performance of a Custom-made Medical Device, "Breast Cancer Locator Guidance (BCL)" System, in Breast-conserving Surgery (BCS)		
	Study ID	CS-BCL-EU2021	Sponsor	CairnSurgical Inc.
	Date	25Nov2022	Version	1.0 Substantial Amendment 1_GERMANY

surgery (BCS) since it has been shown a disease-free survival rate equivalent to those of mastectomy, offering the advantages of cosmetic outcome preservation, a better quality of life and a decrease in psychological morbidities [18].

For non-palpable lesions, a precise preoperative localization technique for the detection of the lesions is needed. Various techniques have been used for identifying non-palpable breast tumors, but the most popular method is the wire-guided localization (WGL). This procedure can easily be performed under ultrasound or mammography guidance and provides real-time control of the wire-needle position, allowing accurate location of the lesion [19]. Over time, though, this procedure has faced several limitations: (i) wire dislodging, migration or wire fracture; (ii) higher patient discomfort and (iii) logistic difficulties, as the wire is to be placed no more than one day before surgery. Moreover, poor cosmetic outcomes have been described and high rates of a non-radical excision of the lesion due to wire dislodging and poor localization have been reported [18]. One of the most important disadvantages of WGL is the relatively large number of patients with positive margins detected at the final pathologic evaluation [5]. Reoperation with further resection is required when a positive margin is present; such a procedure can be both physically and mentally exhausting for the patient and can impair the cosmetic outcome. In addition, reoperation delays adjuvant treatment and is an extra financial expense [5].

In order to reduce the positive margin rate (and therefore the risk of reoperation) and to improve cosmesis (and therefore patient's satisfaction and psychological status), new precise localization tools are needed when performing BCS in patients with non-palpable BC.

CairnSurgical has developed the Breast Cancer Locator (BCL) System to address the limitations of intra-operative scanning and tracking method. In the BCL imaging system, a *supine* MRI is performed several days before surgery and the 3D interactive image of the tumor in the breast (including information on the closest distances from tumor to skin and chest wall) is available to the surgeon in the operating room. Instead of utilizing intra-operative optical scanning and tracking, 3D printing is used to manufacture a patient-specific plastic bra-like form (the BCL), which is placed on the breast. It has holes in its surface, which allow the surgeon to mark the projected tumor edges on the skin. The BCL also has ports, which allow the surgeon to place one hook wire in the center of the MRI-defined tumor and 4 additional bracketing wires to mark the tumor edges inside the breast. The central wire defines a vector from the skin surface to the tumor center, and the bracketing wires give the surgeon guidance within the breast (**Figure 1**).

CairnSurgical has already tested the BCL in a pilot study of 19 Subjects with palpable tumors [20].

No adverse events occurred, and all Subjects had their tumors resected with negative margins. The BCL System is currently under investigation in a prospective, multicenter, 1:1 randomized, controlled trial in 15 centers in the United States. The purpose of that study is to provide evidence that the positive margin rate following BCS using the BCL is not inferior to WGL for surgical guidance.

The BCL System is expected to improve surgical planning and to achieve precise tumor localization, which in turn would result in low re-excision rates, reduced specimen volume and improved cosmesis.

According to Regulation 2017/745 (MDR), manufacturers of medical devices (including custom-made medical devices) shall proactively collect and evaluate clinical data from the use in or on humans of a device which bears the CE marking and is placed on the market or put into service within its intended purpose with the aim

	Study Title	An Interventional, Post-Market Study to Evaluate the Performance of a Custom-made Medical Device, "Breast Cancer Locator Guidance (BCL)" System, in Breast-conserving Surgery (BCS)		
	Study ID	CS-BCL-EU2021	Sponsor	CairnSurgical Inc.
	Date	25Nov2022	Version	1.0 Substantial Amendment 1_GERMANY

of confirming the safety and performance throughout the expected lifetime of the device, of ensuring the continued acceptability of identified risks and of detecting emerging risks on the basis of factual evidence. Since the BCL system is a new custom-made device, the aim of this investigational, post-market clinical investigation is to collect clinical data to confirm the safety and performance of the device in patients eligible for BCS in European countries.

## 2. CLINICAL STUDY DESIGN METHODOLOGY

### 2.1 CLINICAL STUDY OVERVIEW

This is an interventional, post-market, multicentre clinical investigation aimed to enrol patients who require the tumor to be localized in order for the surgeon to perform BCS.

The study will include enrollment at 3 centers in Europe. The countries involved are Germany, Italy, Switzerland. The investigation will be useful to collect Investigational Product (IP)' performance/safety evidence in Europe.

Each Subject, after signing the Informed Consent Form (ICF), will enter into a screening phase (V0) during which several assessments (e.g., demographics, medical history, blood sample collection, evaluation of available prone MRI and core biopsy pathological results) will be conducted. At visit 1 (V1), the Subject will undergo *supine* MRI (10-40 days before surgery), from which the 3D breast image and BCL will be made. At visit 2 (V2) the patient will undergo BCS using the BCL System.

Soon after surgery and prior discharge, potential AEs will be assessed. On the same day, the specimen volume will be determined, and the specimen mammogram will be performed. The excised specimen will be sent to the Pathology lab for analysis. The results of the positive margin rate (PMR), will be obtained within 14 days. At visit 3 (V3), follow-up assessments (including physical examination, and AEs review) will be performed. At the End Of Study (EOS/V4), AEs events will be assessed and patients will be asked to express their satisfaction with the BREAST-Q.

### 2.2 STUDY OBJECTIVES

#### Primary

To evaluate the performance of the BCL in reducing the positive margin rate when the BCL System is used to guide a surgeon performing partial mastectomy.

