Background and Rationale:	
Breast cancer (BC) is the most commonly diagnosed cancer and leading cause of cancer-related death among women. Breast cancer screening programs and improved imaging techniques have contributed to an increased incidence of early-diagnosed (non-palpable) invasive breast cancer (IBC) or ductal carcinoma in situ (DCIS).
 
Breast conserving surgery (BCS), also known as lumpectomy or partial mastectomy, can be considered the gold standard of early stage invasive breast cancer treatment. The primary aims of BCS are 1) to resect the tumor with a surrounding margin of tissue free of cancer cells and 2) to minimize the volume of tissue removed, thereby preserving the overall shape and appearance of the breast. Consequently, BCS results in better physical and psychological well-being when compared to mastectomy procedure. One of the challenges of BCS in non-palpable breast cancer is precise localization of the tumor. The standard method for localization of non-palpable breast lesions is wire-guided localization (WGL) which consists of ultrasound or mammography assisted introduction of the guide wire allowing accurate location of the tumor. Despite the safety and cost-effectiveness of WGL, several complications have been reported included vasovagal reactions, cutting, moving, or loss of the wire, and patient discomfort. Furthermore, WGL may result in excessive removal of breast tissue (therefore, inferior cosmetic outcomes) and high positive margin rates leading to re-operation or an increased risk of local recurrence.
 
CairnSurgical has developed the Breast Cancer Locator (BCL) System. Within the BCL procedure, a supine MRI image is first performed with the breast positioned in its surgical position providing precise detail on the size, shape, depth, edges and 1 centimeter margin for the tumor. These data are then used to analyze the tumor and construct a three-dimensional (3D) tumor model that serves as the basis for two surgical tools. The MRI is also used to manufacture the BCL, a 3D-printed bra-like plastic form that matches the breast surface and designed to guide the surgeon to the precise tumor boundaries and margins. The BCL is constructed pre-operatively, sterilized, packaged and shipped to the hospital of the surgeon prior to the day of the procedure.
 
Dartmouth-Hitchcock Medical Center investigators have recently completed a randomized prospective clinical trial comparing supine MRI, intraoperative scanning and tracking technique to wire localization. One hundred thirty eight (138) subjects were randomly assigned in a 1:1 ratio to partial mastectomy guided by supine MRI or wire localization. The proportion of subjects with positive margins in the MRI guided surgery group was half that observed in wire localization group (9% vs. 19%, <math>p = 0.08</math>).
	

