## 2.3 STUDY ENDPOINTS

### 2.3.1 Primary Endpoints

To evaluate the performance of BCL in reducing the positive margin rate, the proportion of patients with positive margins after partial mastectomy with the BCL, will be obtained (results will be available within 14 days from the day of sample arrival at the pathological lab).

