Barth et al., have recently completed a randomized prospective clinical trial comparing *supine* MRI, intraoperative scanning and tracking technique to wire localization [23]. The study involved one hundred thirty-eight (138) subjects randomly assigned in a 1:1 ratio to partial mastectomy guided by *supine* MRI (group MRI) or wire localization (group WL). Sixty-six (66) percent had invasive breast cancer and DCIS, 22% had invasive cancer and 12% had DCIS. No differences in subject or tumor characteristics existed between groups. The proportion of subjects with positive margins in the MRI guided surgery group was half that observed in group WL: 12% vs. 23% ( $p = 0.08$ ). Mean specimen volumes in groups MRI and WL were not significantly different: 74 vs. 70 ml ( $p = 0.45$ ). Margins for invasive cancers were considered positive if invasive cancer or DCIS cells were present at the edge (on ink) or if DCIS was present  $< 1$  mm from the inked edge. Margins for specimens that contained only DCIS were considered positive if DCIS was present  $< 1$  mm from the inked edge. Consensus guidelines for positive margins were established after the study was initiated [24], [25]. The consensus guideline criteria for a positive margin for invasive cancer was invasive cancer or DCIS at the edge (on ink); the margin for cases that contained only DCIS was considered positive if DCIS was present  $< 2$  mm from the inked edge. Using the new consensus definition of positive margins, the positive margin rate in the MRI group (9%) was lower than those reported in any previously published RCT.

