## 8. APPENDIX

### 8.1 APPENDIX 1: Positive Margin Rate (PMR)

The positive margin rate (PMR) is defined as the proportion of patients with positive margins after breast-conserving surgery (BCS).

According to the consensus guideline criteria (Moran et al. 2014; Morrow et al. 2016) a positive margin is defined as follows:

- Invasive breast cancer (IBC): margins for cases that contain only invasive cancer, or a mixture of invasive cancer and ductal carcinoma in situ (DCIS) are considered positive if invasive cancer or DCIS is present on the inked specimen edge.
- DCIS: margins for cases that contain only DCIS are considered positive if DCIS is present <2 mm from the inked edge. Cases that are mainly DCIS, but also have one or more foci of microinvasion (defined as cancer <1 mm in diameter) will be considered to be DCIS, as per consensus guidelines.

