### 5.1. Treatment Group Names and Labels

Due to the single-arm nature of the stage, no treatment group definition or label is required.

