#### Analysis of Primary Efficacy variable:

To evaluate the performance of BCL in reducing the positive margin rate, exact . 95% Confidence Interval (CI) for positive margin rate (PMR) using the Clopper-Pearson method will be estimated with actual positive margin rate calculated at V2

The primary analysis will be performed on both FAS and PPS. The analysis performed on PPS will be obtained to support the results on FAS.

Moreover, bar plots will be presented to show the positive margin rate distribution.

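### The objective speaks of the BCL reducing the positive margin rate, but this single-arm plan fixes no reference rate, and the protocol prints two candidates (19% and 23%)

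*Protocol*

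**What the plan says.** Protocol section 2.2 sets the primary objective as "To evaluate the performance of the BCL in reducing the positive margin rate when the BCL System is used to guide a surgeon". The endpoint in section 2.3.1 carries the same framing, but what is measured is that "the proportion of patients with positive margins after partial mastectomy with the BCL, will be obtained". SAP section 1.3.1 repeats the objective. The SAP's primary analysis (6.2.1) begins "To evaluate the performance of BCL in reducing the positive margin rate, exact . 95% Confidence Interval (CI" and specifies the Clopper-Pearson method.

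There is no concurrent control. SAP section 5.1 states: "Due to the single-arm nature of the stage, no treatment group definition or label is required". Protocol sections 1.3.2 and 1.3.3 provide for neither blinding nor randomization. Neither document states a hypothesis, a performance goal or a success rule.

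One sentence, in protocol 2.5.1 and again in SAP 1.2.3, makes a comparison. It says that the anticipated upper limit, given as 18%, lies below the rate now seen under standard of care. It names no rate and no source.

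The protocol reports wire-localization rates from one randomized trial of 138 subjects in two places:
- Synopsis, Background and Rationale: the MRI-guided rate "was half that observed in wire localization group (9% vs. 19"%). No margin definition is given.
- Section 2.11.1: the MRI-guided rate "was half that observed in group WL: 12% vs. 23"%. The text ties this to that trial's own margin rule and then adds: "Using the new consensus definition of positive margins, the positive margin rate in the MRI group (9"%) was lower than in earlier published trials. No matching wire rate is given there.

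Appendix 1 adopts the consensus definition. For pure DCIS this reads: "margins for cases that contain only DCIS are considered positive if DCIS is present <2 mm from the inked edge".

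**The concern.** A reduction is a statement relative to something. With one arm and one interval, it can only be relative to an outside rate, and the plan refers to such a rate without fixing it. The study is open-label, so the reference could be chosen after the margin results are known.

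The candidates also differ in definition. Under the earlier trial's own rule, DCIS within 1 mm of the inked edge counted as positive in all cases. Under Appendix 1, invasive and mixed cases are positive only with tumor on ink, while pure DCIS is positive within 2 mm. The second rule is looser for one histology and stricter for the other. Setting this study's rate against 23% would therefore mix two endpoints, with a bias whose direction depends on case mix.

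At stake is whether a report can say that the BCL reduced the positive margin rate, and on what footing.

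**Working it through.** **Inputs.** N = 35 and an assumed true rate of 3%, expected below 5% (protocol 2.5.1, SAP 1.2.3). Exact 95% interval (SAP 6.2.1), taken as two-sided. Candidate references: 19% (synopsis) and 23% (section 2.11.1).

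**Formula.** For x positives among n, the Clopper-Pearson limits are
- lower = Beta⁻¹(0.025; x, n − x + 1)
- upper = Beta⁻¹(0.975; x + 1, n − x)

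The upper limit lies below a reference p₀ exactly when P(X ≤ x | n, p₀) < 0.025.

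**The plan's own figure.** With x = 0.03 × 35 = 1.05, the interval is 0.09% to 15.14%, a width of 15.05%. The stated width of 15% reproduces. The stated upper limit of 18% does not. The exact limit is about 15% (14.92% at x = 1), and 18% equals 3% + 15%, the full width added to the point estimate. This is a separate error, but 18% is the only number that the documents set against standard of care.

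**Reading each count at n = 35 against the two references.** The documents state no rule, so this uses the comparison implied in protocol 2.5.1: is the upper limit below the reference?

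| Positives | Upper 95% limit | Below 19%? | Below 23%? |
|---|---|---|---|
| 0 | 10.0% | yes | yes |
| 1 | 14.92% | yes | yes |
| 2 | 19.16% | no | yes |
| 3 | 23.06% | no | no |
| 4 | 26.74% | no | no |

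Check at x = 2: P(X ≤ 2 | 35, 0.19) = 0.0263, above 0.025; P(X ≤ 2 | 35, 0.23) = 0.0069, below it. Two positives is the only count at n = 35 on which the references disagree.

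**How likely that count is.** P(X = 2) = C(35, 2) p²(1 − p)³³, with C(35, 2) = 595:
- p = 3%: 595 × 0.0009 × 0.97³³ = 0.196
- p = 5%: 595 × 0.0025 × 0.95³³ = 0.274

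The same quantity is the difference in the chance that the upper limit falls below the reference. At a true rate of 3% that chance is 71.7% against 19% and 91.3% against 23%. At 5% it is 47.2% and 74.6%.

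**Sensitivity.**
- Rounding: the gap at 2 of 35 is 19.16 − 19 = 0.16 points. A figure printed as 19% could stand for 18.5% to 19.5%. Against 19.2%, for instance, 2 of 35 would fall below.
- Evaluable n: 2 positives give 20.23% at n = 33, 19.68% at n = 34 and 18.66% at n = 36. At n = 36 the disagreement moves to 3 positives (22.47%). The split changes place but does not disappear.
- Interval: the one-sided 95% upper limit for 2 of 35 is 16.9%, below both references.

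The evaluable number is not settled. The protocol synopsis plans 35 enrolled and section 2.5.5 does not replace withdrawals, whereas SAP 1.2.3 counts 35 operated and assessed.

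**The case against.** The strongest reply is that this is an estimation study. The objective says evaluate, the endpoint is a proportion to be obtained, and the analysis is that proportion with its interval. Protocol section 1.4 gives the formal comparison with wire localization to a separate randomized trial in the United States. The interval will be reported in any case, and readers may set it beside whatever rate they prefer.

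Most of this stands. A reader might infer that the study must show a reduction, and that 2 of 35 would be a success or a failure at the sponsor's choice. The documents do not support that: they contain no pass/fail rule, and the rule used above is only the comparison implied by the sample-size sentence. But if the study only estimates, then *reducing* and the standard-of-care comparison do not belong in the objective, endpoint and analysis text. As written, they invite a conclusion that the design cannot carry.

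It is also fair to say that the numerical split is a knife-edge. It turns on 0.16 points against a rounded figure and on the evaluable n. It shows that the choice can matter, not that it will.

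A reader might further infer that 19% is established as the consensus-definition wire rate, so that a limit of at most 1 positive in 35 should be written into the plan. That goes too far. The synopsis gives 19% without a definition, section 2.11.1 ties only the MRI-arm 9% to the consensus rule, and both pairs carry p = 0.08, so a transcription error cannot be excluded. Nor does any passage say that this trial supplies the rate meant in the sample-size text. The 19% has its own uncertainty too: assuming about 13 of 69 in one arm of a 138-subject 1:1 trial, its exact interval is roughly 10% to 30%.

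Finally, the different cut-offs for invasive and pure DCIS cases might suggest that a subgroup table is required. At the earlier trial's 12% DCIS, 35 × 0.12 is about 4 patients, and 0 of 4 has an exact interval of 0% to 60%. Histology and margin status are already listed per patient, so such a table is a preference.

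**Conclusion.** The point holds as a defect of wording and pre-specification. The plan speaks of reduction without a comparator, refers to an unnumbered standard of care, and prints two rates for it, one of them under a different margin rule. A statement of reduction made under the plan as written would be unsupported or open to choice after the results.

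The size is moderate. At n = 35 the two references disagree on one count, 2 positives, with probability 20% at a true rate of 3% and 27% at 5%. This assumes a two-sided exact 95% limit, exactly 35 evaluable patients and references taken as printed. That 19% matches Appendix 1 is an inference from its pairing with 9%, which the sponsor must confirm. That 23% was obtained under a different rule is stated in section 2.11.1.

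The planned estimate and interval are sound. What needs correcting is the claim attached to them.

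**What to change.** Reword the objective and endpoint in the protocol (synopsis, 2.2, 2.3.1) and SAP (1.3.1, 6.2.1) as: *to estimate the positive margin rate with the BCL*. State that no conclusion of reduction will be drawn from this study alone. Remove the standard-of-care sentence from protocol 2.5.1 and SAP 1.2.3, or complete it as below, and correct its 18% upper limit in either case.

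If the sponsor keeps a comparison with standard of care, name one reference rate before database lock, with its source and margin definition. The definition should match Appendix 1, which rules out the 23%. Adopt 19% only after confirming from the trial report that it is the consensus-definition wire rate. Describe the BCL rate as lower only if the exact 95% upper limit, at the actual evaluable n, is below that reference. No fixed count of positives is needed.

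The SAP is at version 0.1 and cites protocol version 2.0, which was not among the documents supplied, so the current protocol text should be checked and changed in step. The cost is wording only, with no added patients, procedures or data. The sponsor gives up the looser 23% comparison and the unqualified word *reducing*.
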